1. INTRODUCTION

A. BACKGROUND AND RATIONALE

New-onset postoperative atrial fibrillation (POAF) commonly complicates cardiac surgery, affecting between 20 and 50% of patients,¹ with an even higher risk for patients undergoing combined coronary artery bypass graft (CABG) and/or valve replacement procedures.^{2,3} The spectrum of POAF varies from self-limited episodes to persistent AF requiring antiarrhythmic drug therapy (AAD) and cardioversion.

Overall, POAF portends significantly worse clinical outcomes, including an up to four-fold increased risk of stroke and doubling of both all-cause 30-day and 6 month mortality.⁴ In addition, POAF is independently associated with prolonged intensive care unit (ICU) stays, longer overall duration of hospitalization (extending length-of-stay by 2 to 5 days), and significantly increased costs by \$10,000-20,000, even during the index hospitalization.^{4,5} POAF usually occurs between 2 and 4 days after surgery, with a peak incidence on postoperative day 2.⁶ The pathogenesis of POAF in the cardiac surgical setting remains poorly understood, although there is data to suggest that autonomic imbalance during the post-operative period may play a key role for some patients.¹

Peripheral vagal nerve stimulation can alter central parasympathetic cardiac inputs, leading to reduced heart rate along with reduced dispersion of atrial effective refractory periods (AERPs), lowering the risk of AF.^{7,8} While direct vagal nerve stimulation has an established role in the treatment of intractable epilepsy and treatment-resistant depression,^{9,10} its application for POAF has been limited due to its invasive nature and increased risks.

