2. STUDY DESIGN

Study design: Single-blind study. Patients will be randomized, to LLTS versus sham procedure, and remain blinded to their treatment allocation. Both treatment options will utilize similar equipment, namely the use of alligator clips which will be placed on the tragus and earlobe of the right ear for patients (see Appendix A, Figure 2). The distinction is only that in patients assigned to LLTS, they will be initiated on therapy at the time of device placement.

Prior to cardiac surgery, the discomfort threshold of both left and right tragus stimulation will be determined for all participating patients. Intermittent electrode signals, or microcurrents, are delivered at 20 Hz with 200 μ sec pulse width with variable microampere (mA) output. The discomfort threshold is defined as the stimulation intensity in mA at which point patients experience discomfort. The stimulation intensity used in the study will be set just below the discomfort threshold, as established from prior work.¹⁵ The clip will then be placed on the patient's ear at the end of surgery. After surgery is completed, the clip will then be removed and replaced on the contralateral ear. Stimulation will then continue, one ear alternating with the other, every 4 hours for a total of 48 hours. It is possible that the threshold can change during the post-operative period. If the patient shows any sign of discomfort from stimulation, the intensity of stimulation will be reduced to a level at which signs of discomfort disappears.

Follow-up will be performed with 14-day event monitor (i.e. Zio patch or CardioNet event monitor) at the time of discharge.

Electrocardiography (i.e. ECG) will be performed pre-procedure and prior to hospital discharge. Echocardiography will be assessed prior to study initiation and when clinically available in follow-up.

Duration of study: 1 month

Primary endpoints: A combination of clinical and electrocardiographic endpoints will be prospectively studied. These include:

- **Clinical:** Primary clinical endpoint is time to inpatient AF (length of stay >5 days). Secondary endpoint is any occurrence of AF during 14 day post procedure monitoring.
- **Electrocardiographic:** Arrhythmia occurrence (i.e., AF, nonsustained VT, VT or VF requiring device therapy) will be documented throughout the study period

Primary safety endpoint: Procedure-related complications will be assessed prospectively both acutely and throughout the study period, including:

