- **Procedure related:** pain, tragus site abrasion or bruising

Randomization scheme: Patients will be allocated to LLTS or sham in a 1:1 ratio at time of implant based on random number generator.

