5. STUDY PROCEDURES

Pre-Stimulation:

- Patients will be screened for study
- Discomfort threshold bilaterally will be measured (20 Hz) for 5 minutes
- Pre-implant ECG reviewed (to be performed on day of screening)
- Baseline transthoracic echocardiogram (TTE) reviewed (does *not* need to be performed during inpatient hospitalization; outpatient or outside-hospital TTE report may also be performed)
- NYHA functional class to be determined by treating physician
- Operating physician will be informed of patient randomization allocation to facilitate planning of procedure

Randomization, Implant, and Periprocedure Care:

- LLTS or sham will instituted upon arrival in PACU/recovery after surgery with right sided LLTS. The site of stimulation will alternate every 4 hours between right and left tragus for total stimulation duration of 48 hours.
- Postoperative care for the cardiac surgical patient will be performed as per routine standard of care by the treating primary team
- The patient will be maintained on telemetry during the entire inpatient hospitalization
- Telemetry will be checked daily to evaluate for any new-onset AF
- Predischarge ECG will be performed at the time of hospital discharge
- The patient will be fitted with a 14-day event monitor (i.e. Zio patch or Cardionet monitor) at the time of discharge or to be mailed to the patient/picked-up by patient immediately after discharge on a weekend discharge day
- Blood will be collected for C-reactive protein measurement to assess inflammation per routine lab assessments

Follow-Up Visit (can be performed between 2 weeks and 1 month after discharge):

- The patient will return the 14-day monitor, if not already mailed back
- Routine clinical check as per primary team

Future contact:

- Patients will be asked to participate in an extended registry (protocol IRB16-0272) to evaluate longer-term clinical outcome after study completion. Patients will be asked to sign a separate consent form for participation in this study.

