6. STATISTICAL PLAN AND CONSIDERATIONS

Primary Outcome:

1. Time to the first episode of AF >30 seconds during inpatient admission or within 14-day monitoring period

- a. In hospital: full-disclosure telemetry
- b. Time to AF will be assessed by physicians blinded to randomization
- 2. Extended hospitalization of >5 days

Secondary Outcomes:

- 1. Overall AF burden, as assessed by 2 week monitor (CardioNet or Zio Patch) upon discharge
- 2. Inflammatory markers: C-reactive protein (ordered if clinically indicated)
- 3. Actionable AF: antiarrhythmic use (including rate-control meds), CDV, anticoagulation, use of inotropes for BP support during AF
- 4. Stroke or transient ischemic attack (TIA)
- 5. All cause of mortality

Sample size estimation:

Assuming a two-armed study with composite endpoint of occurrence of AF or >5 days hospitalization, whereby the treatment group will have 50% likelihood of the event occurring and a control group will have 20% likelihood of the event occurring, as well as a 10% dropout rate, we will be able to detect differences in 80 patients (40 in each arm). Under these assumptions and using two-sided Z-Test with unpooled variance to compare the changes between these two groups, we will have 80% power ($\alpha=0.05$) to detect a difference between the group proportions of 0.30. PASS software Version 15 (NCSS, LLC, Kaysville, UT) was used to calculate the statistical power.

Statistical methods:

Patients will be studied based on the randomization allocation. Patients who refuse to continue with study treatment (i.e. they refuse to wear ear clip) during time of therapy will be analyzed as intention-to-treat per allocation group. Fisher's exact or the Chi-Square test will be used for categorical variables, and continuous parameters will be compared by the two-tailed unpaired Student's t test and the F test for analysis of variance (ANOVA), as needed. Kaplan-Meier method will be used for computing the event free survival curves. Each strategy will be compared within this cohort of patients for its impact on percent incidence of POAF and length of stay. Multiple logistic regression and multiple regressions using the Cox proportional hazards model will be performed to determine the independent association of each of the demographic variables with clinical outcome.

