8. SAFETY AND ADVERSE EVENTS

Safety:

As noted above, periprocedural complications will be logged with respect to procedure, system-related, and lead-related events. All complications will be independently reviewed at the midpoint by the primary investigator (PI). Should there be a trend towards increased complication risk, the study will be halted.

Adverse Events:

As noted above, all adverse events associated with devices will be monitored periprocedurally and continuously through the study. The PI will independently review all events after randomization of 20 subjects in order to make a determination for continuance.

Adverse Effect Documentation:

1. Sinus bradycardia or AVB after stimulation
2. Discomfort or possible skin abrasion due to tragus stimulation
3. Major organ-system failure
4. Death

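### Sinus bradycardia and AV block are named adverse effects, but no listed safety component, telemetry review or blinded read covers them, so they may be under-counted or counted differently by arm

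*Combined protocol and SAP*

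**What the plan says.** **The risk is acknowledged.** Section 1 states "Peripheral vagal nerve stimulation can alter central parasympathetic cardiac inputs, leading to reduced heart rate". Under Adverse Effect Documentation, Section 8 names sinus bradycardia or AV block following stimulation as its first item.

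**The endpoints do not list it.** Section 2 introduces the primary safety endpoint with "Procedure-related complications will be assessed prospectively both acutely and throughout the study period, including", and the items that follow are "pain, tragus site abrasion or bruising". The electrocardiographic endpoint in the same section reads "Arrhythmia occurrence (i.e., AF, nonsustained VT, VT or VF requiring device therapy) will be documented throughout the study period".

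**The rhythm data will exist.** Section 5 says "The patient will be maintained on telemetry during the entire inpatient hospitalization", and Section 6 gives the source for the AF outcome as "In hospital: full-disclosure telemetry". The only telemetry review described in Section 5 is "Telemetry will be checked daily to evaluate for any new-onset AF".

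**Other scheduled checks (Appendix C).** ECGs fall at screening and on the day of discharge. Clinical evaluation with vital signs and the adverse-event row are both marked at surgery, on postoperative days 1-2, at discharge and at follow-up.

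**Logging and review.** Section 8 says "periprocedural complications will be logged with respect to procedure, system-related, and lead-related events". It also says that device-associated adverse events are monitored continuously. Section 10 has the PI compare complications and adverse events between the groups at the midpoint, with provision to halt.

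**Blinding.** The trial is single-blind, and Section 5 has the operating physician told the allocation. Section 6 specifies blinded physicians for time to AF and for nothing else.

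**The concern.** The protocol names a cardiac adverse effect of stimulation but does not carry it into the parts of the plan that decide what is measured and reported. No definition is given (rate, grade of block, duration or time window), no telemetry review is assigned to it, and it is not a listed component of either the safety or the electrocardiographic endpoint.

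Two things are at stake. The first is completeness: a slow rate or a conduction disturbance that comes and goes between vital-sign checks may leave no entry in the adverse-event record, although the telemetry holds it. The second is comparability: where an event has no definition and some staff know the allocation, the threshold for writing it down can differ between LLTS and sham. A report on the listed primary safety components would then be silent on this effect, and the adverse-event table beside it could look more reassuring than the data justify.

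**Working it through.** **Step 1. Set the measurement provisions side by side.**

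| Provision | Where | Covers bradycardia/AV block? |
|---|---|---|
| Adverse effects to document | Section 8 | Yes, named; not defined |
| Primary safety endpoint, listed items | Section 2 | No; all are local to the ear |
| Electrocardiographic endpoint | Section 2 | No; AF, nonsustained VT, VT/VF |
| Daily telemetry check | Section 5 | No; new-onset AF |
| ECG | Section 2, Appendix C | Screening and discharge only, so outside the 48 h unless discharge falls within it |
| 14-day monitor | Section 5 | Starts at or after discharge |
| Vital signs and adverse-event checks | Appendix C | Partly; intermittent, on Day 0 and days 1-2 |
| Complication log categories | Section 8 | None is for rhythm; one is for leads, and the device is an ear clip |
| PI review by arm | Section 10 | Yes, for whatever has been recorded |
| Blinded assessment | Section 6 | No; stated for time to AF |

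The event is named at the start of the chain and reviewed at the end. The step between, a defined and systematic search of the recording, is missing.

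**Step 2. The number of patients.** The documents give no figure for safety. Their only sample-size figure is for efficacy, and it reproduces. With event proportions 0.50 and 0.20, unpooled variance, two-sided alpha 0.05 and 80% power:

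n per arm = (1.960 + 0.842)² × (0.50×0.50 + 0.20×0.80) / 0.30² = 35.76, rounded up to 36. Then 36 / (1 − 0.10) = 40 per arm, or 80 in total.

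So 40 LLTS patients are planned, 36 if the 10% dropout occurs.

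**Step 3. What incomplete detection would do.** The true rate r and the detected fraction d are assumptions; the documents give neither. The chance of at least one recorded event in 40 is 1 − (1 − r×d)^40.

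| True rate r | d = 1 | d = 0.5 | d = 0.25 |
|---|---|---|---|
| 5% | 87% | 64% | 40% |
| 10% | 98.5% | 87% | 64% |

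With 36 patients and full detection, the figures are 84% at 5% and 97.7% at 10%.

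**Step 4. What full detection would not do.** If no event is seen in 40, the upper limit of the two-sided 95% exact interval is 1 − 0.025^(1/40) = 8.8% (9.7% for 36). For a between-arm comparison, take the two-proportion Z-test with pooled variance under the null and 40 per arm:

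- 5% versus 15%: Φ[(0.10 − 1.96×0.0671)/0.0661] = Φ(−0.476) = 32%.
- 10% versus 20%: Φ[(0.10 − 1.96×0.0798)/0.0791] = Φ(−0.715) = 24%.

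A systematic read therefore makes the count complete and comparable. It does not give the trial power to exclude a difference.

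**The case against.** A reader might infer that bradycardia and AV block will be found only if ward staff volunteer them, that a rhythm event cannot reach the halting decision, or that the safety result will say nothing about the heart. The documents support none of these.

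- Appendix C schedules vital signs and an adverse-event check on the day of surgery and on postoperative days 1-2, inside the stimulation window. With the named item in Section 8, that is planned collection, not spontaneous reporting.
- Section 10 has the PI compare all adverse events by arm and allows a halt, and Section 8 adds a review of all events after 20 subjects. The three-category complication log is not the only route.
- The safety list is introduced by an open word, so unlisted procedure-related events are not excluded.
- AF, ventricular arrhythmia, stroke or TIA, and death are all recorded elsewhere in the plan.

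Two further points are fair. The heart-rate statement in Section 1 concerns peripheral vagal stimulation in general, and the same section credits LLTS with both anticholinergic and antiadrenergic effects, so the mechanism does not point simply to bradycardia. This point therefore rests on Section 8 naming the event. Also, one or more cases in the LLTS arm would not show harm, because sham patients may have bradycardia after surgery too.

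What remains is narrower. Intermittent vital signs can miss transient bradycardia and do not establish AV block. The open wording gives no definition or method. The reviews in Sections 8 and 10 can be no better than the records that reach them.

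**Conclusion.** The point holds as a gap in systematic, blinded ascertainment, not as an absence of monitoring. Transient bradycardia or AV block could be under-counted or counted unevenly by arm, and the listed primary safety components would not report it.

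The size cannot be derived from the documents. If the true rate is 5-10% and only a quarter of events are captured, the chance of recording any event in 40 LLTS patients falls from about 87-98% to about 40-64%. The rates and the detected fraction are both assumptions, and the figures illustrate the effect; they do not estimate this plan's detection rate.

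The primary efficacy analysis is unaffected. The change is worth making because the recording already exists and the cost is low.

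**What to change.** 1. **Section 2:** list sinus bradycardia and AV block in the primary safety endpoint, with event definitions prespecified by the investigators. Report the 48-hour stimulation window separately from the rest of the stay, so that later time without stimulation does not dilute a difference.
2. **Sections 5 and 6:** extend the daily telemetry review to these events in both arms, and have them read blinded to allocation by the physicians who already assess AF that way.
3. **Section 8:** replace the system and lead categories of the complication log with ones that fit an ear-clip device (ear-site, rhythm, other), and align the log with the all-adverse-event review in Section 10.

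**Cost:** protocol wording, agreed definitions, and a few more minutes per telemetry review. No new test or recording is needed. The report should state that 40 per arm is too few to establish that the arms do not differ, and should give the counts with exact confidence intervals.

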3. SUBJECT SELECTION AND WITHDRAWAL

Sites:

Subjects selected for study will be recruited from the University of Chicago Medical Center (Chicago, IL).

Eligibility:

Eligible patients will be all patients undergoing CABG and/or valve surgery.

Inclusion Criteria:

1. Patients ≥ 18 years of age, <90 years of age
2. Estimated life expectancy of at least 1 year at the time of enrollment
3. History of sinus rhythm or paroxysmal atrial fibrillation

Exclusion Criteria:

1. Patients ≥ 90 years of age, <18 years
2. Patients with known prior history of persistent or permanent AF
3. Atrial Fibrillation occurrence within the last 24 hours of procedure
4. Urgent or Emergency cases
5. Pregnant patients
6. Patients undergoing the following cardiac procedures: heart transplant, pulmonary thromboendarterectomy, isolated aortic arch procedures, congenital heart disease, ventricular assist device insertion, extracorporeal membrane oxygenation insertion, and surgical AF ablation
7. Antiarrhythmics prior to surgery (Class I and Class III)
8. High degree AV block requiring temporary pacing
9. MAZE procedure

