Transcutaneous low-level tragus stimulation (LLTS), however, has recently emerged as a novel, entirely noninvasive means to achieve vagal nerve stimulation, which achieves anticholinergic and antiadrenergic effects.¹¹ The auricular branch of the vagus nerve localizes to the skin near the anterior protuberance of the outer ear, called the tragus. LLTS has been shown to significantly suppress AF inducibility, reduce overall AF duration, and reduce the production of inflammatory cytokines (i.e., TNF-alpha and C-reactive protein) in acute studies.¹²⁻¹⁵ Furthermore, it may have additional benefits in inducing autonomic remodeling, as well as reducing ventricular arrhythmia.¹⁶ The Parasym device delivers LLTS through the skin via the outer ear (see Appendix A, Figures 1-2). It has been used in a variety of medical treatments, including tinnitus, depression, anxiety, and rheumatoid arthritis. We seek to evaluate the role of LLTS in preventing POAF, reducing AF duration, reducing average length of stay, and reducing overall arrhythmia incidence after cardiac surgery.

B. OBJECTIVES

We hypothesize that:

- a. In patients undergoing cardiac surgery (i.e., CABG and/or valve surgery), new-onset POAF is common
- b. LLTS is a simple, noninvasive and effective means to reduce the incidence of POAF, reduce overall AF duration, and reduce incidence of significant ventricular arrhythmias (i.e., nonsustained or sustained VT/VF)
- c. Use of LLTS in the inpatient setting leads to reduced overall AF and reduced AF duration in the 30-day period after cardiac surgery

Specific aims:

Aim 1: To determine the overall rate of successful LLTS in the inpatient setting. Patients randomized to LLTS will undergo continuous stimulation for two inpatient days. Tolerance of LLTS versus sham will be assessed.

Aim 2: To assess the impact of LLTS on acute and short-term outcomes. Acute outcomes include the incidence of inpatient POAF during the index hospitalization, length of hospital stay, overall AF duration, and incidence of nonsustained or sustained VT/VF. Short-term outcomes include incidence of AF as assessed by 14-day monitor (i.e. Zio patch or CardioNet event monitor) upon discharge.

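### The arms are to be compared without adjustment, although surgery type and prior paroxysmal AF are pooled under unstratified randomisation: valid on average, but naming two covariates for the treatment effect would be a cheap, modest improvement

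*Combined protocol and SAP*

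**What the plan says.** - **Who is enrolled.** Section 3 accepts patients with "History of sinus rhythm or paroxysmal atrial fibrillation" and covers CABG, valve surgery or both. Persistent or permanent AF, AF in the 24 hours before the procedure, and Class I or III antiarrhythmics before surgery are exclusions.
- **What is said about risk.** Section 1.A gives an overall POAF risk of 20–50%, "with an even higher risk for patients undergoing combined coronary artery bypass graft (CABG) and/or valve replacement procedures". It gives no figure by surgery type. No section gives the expected share of patients with prior paroxysmal AF, or their risk.
- **How patients are allocated.** Section 2 says 1:1, "based on random number generator", and names no strata or blocks.
- **How the arms are compared.** Section 6 sizes the trial "using two-sided Z-Test with unpooled variance to compare the changes between these two groups". Its methods paragraph names Fisher's exact or chi-square tests, t tests and Kaplan-Meier curves. It also plans multiple logistic and Cox regression, for the stated purpose of relating demographic variables to outcome. AF history, surgery type and a treatment term are not mentioned.
- **New-onset wording.** Hypothesis (a) in Section 1.B is that "new-onset POAF is common", and the daily telemetry check in Section 5 looks for new-onset AF. The primary outcome in Section 6 is any first AF episode longer than 30 seconds, so a recurrence in a patient with known paroxysmal AF counts.

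**The concern.** Surgery type is tied to POAF risk by the protocol itself, and prior paroxysmal AF may plausibly predict it too. With 40 patients per arm and no stratification, either factor can fall unevenly by chance, and an unadjusted comparison carries that imbalance into the treatment estimate. Because the planned regressions name neither covariates nor a treatment term, the choice between an adjusted and an unadjusted headline would also be made after the data are seen. Two things are at stake: the reliability of a borderline result in one small trial, and a little power that could be had without extra patients.

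**Working it through.** **1. The plan's sample size reproduces.** Inputs from Section 6: 50% versus 20%, two-sided alpha 0.05, 80% power, unpooled variance, 10% dropout.

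n = (1.960 + 0.842)² × (0.5×0.5 + 0.2×0.8) / 0.30² = 35.76, so 36 per arm. Then 36 / 0.90 = 40 per arm, 80 in total, as stated. Power at 36 per arm is 80.3%. Expected events: 36 × (0.50 + 0.20) = 25.2. (As printed, the higher rate belongs to the treatment arm, which contradicts the hypothesis. That is a separate point and does not change n.)

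**2. How likely is an imbalance?** Assume 12 of 80 patients (15%) have prior paroxysmal AF. The first figure in each range treats the arms as exactly 40/40 (hypergeometric), the second as independent coin tosses (binomial).

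- 8:4 or worse, either direction: 35–39% (binomial: 2 × 794/4096 = 38.8%).
- 9:3 or worse, either direction: 11.5–14.6% (binomial: 2 × 299/4096 = 14.6%).
- 9:3 or worse in one given direction: 5.7–7.3%.

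For a general baseline factor, the chance that two arms of 40 differ by at least 10 points depends on its assumed prevalence:

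| Prevalence | 5% | 10% | 20% | 30% | 50% |
|---|---|---|---|---|---|
| Chance of ≥10 points | 7% | 19% | 33% | 39% | 43% |
| Chance of ≥20 points | 0.03% | 0.5% | 3.5% | 6.7% | 9.3% |

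**3. How far does it move the arms?** With no treatment effect, shift = difference in factor prevalence between arms × risk difference between factor levels. At 9:3 the first term is (9 − 3)/40 = 0.15. Let p0 and p1 be the risks without and with AF history, with overall risk 0.35 = 0.85·p0 + 0.15·p1.

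- Odds ratio 3: p0 = 0.310, p1 = 0.574; shift = 0.15 × 0.264 = 4.0 points.
- Odds ratio 5: p0 = 0.293, p1 = 0.674; shift = 0.15 × 0.381 = 5.7 points.

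Over an overall risk of 30–50% the range is 3.8–5.7 points. That is 13–19% of the 30-point design effect (3.8/30 to 5.7/30), or about two patients in an arm of 40 (0.038 × 40 = 1.5 to 0.057 × 40 = 2.3).

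**4. What does it do to the error rate?** At a 9:3 split, overall risk 35% and odds ratio 3–5:

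- Unpooled Z test: 5.5–7.2% in the favoured direction (nominal 2.5%) and 0.9–0.5% in the other, about 6.4–7.6% in total.
- Fisher's exact test: 3.6–4.4% two-sided.

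Over all randomisations, without conditioning on a bad split:

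- Exact calculation, 40 per arm, 35–50% risk: 5.2–5.7% for the unpooled Z test and 2.8–3.3% for Fisher's.
- Simulation (20,000 runs): 5.4–5.8% unadjusted and 5.3–5.6% adjusted.

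**5. What does adjustment gain?** At the design rates with 36 per arm, power goes from about 79–80% unadjusted to 80–84% adjusted. This range covers an assumed odds ratio of 3–5 for AF history and 1.5–2.5 for surgery type, and a single factor with 20–50% prevalence and a risk difference of 0.30–0.40.

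**6. What does it cost in events?** Arm plus two covariates is three parameters: 25.2 / 3 = 8.4 events each.

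**The case against.** The strongest reply is that nothing here is an error. Simple randomisation with an unadjusted test is a legitimate design. Its type I error is near 5% overall, and with Fisher's test, which Section 6 lists first, it stays below 5% two-sided even at a 9:3 split. The inflated figures arise only with the Z test, after conditioning on an unlucky draw and, for the largest, on one direction. All of this stands, and it sets the size of the point.

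Four stronger readings are tempting but are not supported:

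- *That imbalance could pass as the treatment effect.* A shift of 4–6 points cannot produce a 30-point difference.
- *That the protocol identifies prior paroxysmal AF as a strong predictor.* It appears only as an eligibility condition, and the exclusions narrow that subgroup. Section 1.A links risk only to surgery type, and only in words.
- *That no adjustment is planned.* Logistic and Cox models are planned; the gap is that they are not assigned to the treatment effect.
- *That eligibility contradicts the hypothesis.* Hypothesis (a) is descriptive. The treatment hypothesis (b), the objective and the primary outcome concern POAF or AF without the new-onset restriction. What remains is mostly loose wording.

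The objection does not answer the case for pre-specification: the planned models leave the covariates and the role of treatment open.

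**Conclusion.** The point holds as a recommended improvement, not as a flaw in validity. Section 6 specifies only unadjusted treatment comparisons in a small, unstratified trial that mixes surgery types which the protocol says differ in risk and includes patients with prior paroxysmal AF. A chance 9:3 split would shift the arms by about 4–6 points and could tip a borderline result. That size rests on an assumed 15% prevalence and an odds ratio of 3–5. If prior paroxysmal AF is rare the matter shrinks: at 5% prevalence an imbalance of 10 points or more has only a 7% chance. The gain from adjustment is modest, about 79–80% to 80–84% power at unchanged N, and depends on the same kind of assumption. A reader should not infer that the overall false-positive rate is inflated or that the unadjusted result would be misleading as a rule.

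**What to change.** - State in Section 6 that the treatment effect on time to AF is estimated from a Cox model, and on the binary composite from a logistic model, each with arm, AF history (none versus paroxysmal) and surgery type (isolated CABG versus any valve or combined) as fixed covariates. Keep the unadjusted comparison as supportive. The surgery cut is one reading of an ambiguous sentence in Section 1.A, so the investigators should settle it before unblinding.
- Report AF in patients without prior AF as a sensitivity analysis, or reword the new-onset passages.
- Optional, if enrolment is still open: stratify randomisation by AF history, with blocks of varying size. First reconcile the timing, since Section 2 places allocation at the time of implant and Appendix C marks it at screening, before the procedure.

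The cost is mainly wording, with no extra patients or visits. Rhythm history is needed for eligibility and the planned operation is known beforehand, but both should be listed explicitly as baseline data items. The downsides are that the effect becomes conditional on the covariates and that about eight events per parameter leaves no room for more of them; a Cox model for AF alone may have fewer.
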